#### **8.4.1 Prior Medications**

Prior medications will be presented separately from concomitant medications in a summary table. Any medication with a stop date prior to the date of the first dose of the study will be considered a prior medication.

#### **8.4.2 Concomitant Medications**

Any medication that is ongoing, has a start date on or after the first dose of study, or a stop date on or after the first dose date will be considered a concomitant medication. If stop date is missing, the medication is considered as ongoing.

Prior and concomitant medications will be summarized for treatment groups of the previous trial and overall by ATC level 4 term and preferred name. These summaries will present the number and percentage of subjects using each medication. Subjects may have more than 1 medication per ATC class and preferred name but will only be counted once in the summary.

Prior and concomitant medications and concomitant procedures will be listed for all subjects.

### **9 Efficacy Analyses**

All efficacy analyses will be analyzed based on FAS. The PP Analysis Set will be used as needed for supportive analysis of the primary endpoint. There are two types of Baselines (Trial Baseline and HZN-825 Baseline) used in analyses as appropriate. Because this is an open-label, single-arm trial, no formal statistical analyses will be conducted. The comparisons between the treatment groups and p-values are for descriptive purpose.

#### **9.1 Primary Efficacy Endpoint Analysis**

The primary efficacy endpoint will be the change from both Baselines (Trial Baseline and HZN-825 Baseline) in FVC% predicted at Week 52.

A mixed model for repeated measures (MMRM) will be fit to the data for descriptive purposes using observed change in FVC % predicted values from all planned post-Trial Baseline assessments (Weeks 16, 28, 40 and 52). The model will include the fixed covariates factors used for stratifying randomization (use of mycophenolate mofetil [yes/no] and presence of ILD [yes/no]) in the previous trial, the treatment received in the previous trial, treatment by Visit Week and Visit Week. The Trial Baseline value will be used as a continuous covariate. An unstructured covariance matrix will be used for the primary

analysis; if the model does not converge, other covariance matrices or descriptive statistics will be considered. The least squares mean (LS mean) difference in change from Trial Baseline to Week 52 in MMRM will be estimated from this model. For subjects with missing data at 1 or more time points, the available data will be included in the analysis. A similar process for the FVC % predicted for the change from HZN-825 Baseline will also be performed.

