## 7.2 Rationale for this Trial

[figure not shown]
Fipaxalparant (HZN-825) is under investigation as a novel therapy for SSc because it selectively antagonizes LPAR1, which has been shown to be associated with skin, pulmonary, cardiac, peritoneal and tubulointerstitial fibrosis, and may be a new therapeutic target for treating fibrotic diseases, including SSc. Details are provided in the current version of the Investigator's Brochure.

This trial is designed as an open-label extension of HZNP-HZN-825-301, in which subjects received fipaxalparant (HZN-825) 300 mg QD, fipaxalparant (HZN-825) 300 mg BID or placebo during the 52-week double-blind Treatment Period. Subjects in this extension trial will receive open-label fipaxalparant (HZN-825) 300 mg BID. This extension trial will allow subjects to have up to 24 months of treatment with fipaxalparant (HZN-825), as well as limit the duration subjects are exposed to placebo. This trial will allow examination of long-term safety and tolerability of fipaxalparant (HZN-825), assessment of the durability of response and/or improved response in subjects who received fipaxalparant (HZN-825) in HZNP-HZN-825-301 and evaluation of efficacy in subjects who received placebo in HZNP-HZN-825-301.

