### 4 Study Design

[figure not shown]
This is an open-label, repeat-dose, multicenter extension trial of HZNP-HZN-825-301.

Subjects who complete the double-blind Treatment Period (Week 52) in Trial HZNP-HZN-825-301 will be eligible to enter this 52-week extension trial. Subjects who enter this extension trial will complete the Week 52 Visit activities in HZNP-HZN-825-301 and will not complete the Safety Follow-up Visit 4 weeks after the last dose of trial drug in HZNP-HZN-825-301.

On Day 1 (Week 52 Visit of HZNP-HZN-825-301), subjects will receive their first dose of HZN-825 in this extension trial at the clinic and will participate in trial visits at Week 4 and every 6 weeks thereafter until Week 52. The Week 52 Visit activities in HZNP-HZN-825-301 will serve as Trial Baseline for this extension trial.

If a subject prematurely discontinues trial drug, he/she will be asked to remain in the trial, participating in the scheduled trial visits through Week 52. If a subject prematurely discontinues trial drug and does not wish to continue in the trial, he/she will return for a clinic visit and undergo the Week 52 assessments. Subjects will participate in a Safety Follow-up Visit 4 weeks after the last dose of HZN-825.

An overview of the trial design is presented in Figure 1.

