## 6 General Considerations

SAS version 9.4 or higher will be used to perform all data analyses.

Summaries of continuous variables will be in terms of the number of observations, mean, standard deviation, median, first quartile (Q1), third quartile (Q3), minimum and maximum. Other descriptive statistics (e.g. standard error, coefficient of variation) may be reported when appropriate. Categorical variables will be summarized using frequency counts and percentages. Analyses that use other descriptive statistics will have the specific descriptive statistics identified with the analysis in the applicable SAP section. All confidence intervals, statistical tests, and P-values will be reported at 2-sided 5% significance level unless otherwise specified.

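### The MMRM fits a single Trial Baseline slope across visits, although Trial Baseline is a 301 outcome that can differ between prior arms; a baseline-by-visit term would remove a possible small bias in the descriptive Week 52 LS mean difference.

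*SAP*

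**What the plan says.** SAP 9.1 models observed change in FVC % predicted at Weeks 16, 28, 40 and 52. The fixed effects are the two 301 stratification factors (mycophenolate mofetil use and presence of ILD) and "the treatment received in the previous trial, treatment by Visit Week and Visit Week". Baseline enters separately: "The Trial Baseline value will be used as a continuous covariate". On covariance, "An unstructured covariance matrix will be used for the primary" analysis. The output named is a Week 52 contrast: "The least squares mean (LS mean) difference in change from Trial Baseline to Week 52 in MMRM will be estimated from this model". Protocol 9.6.3 specifies the same model. Neither document lists a baseline-by-visit term.

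SAP 4 says what Trial Baseline is: "The Week 52 Visit activities in HZNP-HZN-825-301 will serve as Trial Baseline for this extension trial". Protocol 7.2 says what came before it: subjects had received fipaxalparant "300 mg QD, fipaxalparant (HZN-825) 300 mg BID or placebo during the 52-week double-blind Treatment Period".

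SAP 9 states that no formal analysis is intended and that group comparisons and p-values are descriptive. They will still be reported: "All confidence intervals, statistical tests, and P-values will be reported at 2-sided 5% significance level unless otherwise specified". SAP 9.2 carries the 9.1 approach over to the continuous exploratory endpoints.

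**The concern.** With treatment-by-visit in the model, the Week 52 LS mean difference is in essence the raw Week 52 difference in mean change minus the fitted baseline slope times the difference in mean baseline. In a randomised trial the baseline difference is near zero by design, so an imperfect slope does little harm.

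Here Trial Baseline is measured after a year on QD, BID or placebo. If the drug affected FVC in 301, the prior arms will differ at Trial Baseline, and any error in the Week 52 slope passes into the Week 52 contrast multiplied by that difference. A slope that changes over time is plausible: if the correlation with baseline decays, regression to the mean grows with each visit.

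What is at stake is the one MMRM estimate that SAP 9.1 names for the primary endpoint, and the same estimate for the exploratory endpoints that reuse the model. Protocol 7.2 lists durability in prior-drug subjects and efficacy in prior-placebo subjects among the aims, so readers will look at these group contrasts.

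**Working it through.** The plan gives no figure to reproduce: no sample size, SD, correlation or effect size is stated. From the documents come the model terms, the four visits, the unstructured covariance and the definition of Trial Baseline. Every numeric input below is an assumption.

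**Formula.** Let the true model for two prior arms be change_t = a_t + g_t·arm + b_t·B + e_t, with residual covariance W over the four visits. Fitting one slope gives, in large samples,

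b* = (1ᵀW⁻¹b) / (1ᵀW⁻¹1),

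a weighted sum of the visit slopes. The Week 52 LS mean difference is then off by

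bias = (b52 − b*) × δ,

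where δ is the between-arm gap in mean Trial Baseline. (The stratification factors are left out; with them, δ is the gap that remains after adjusting for them.) The bias is zero if b_t is constant or if δ = 0.

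**Check 1: residual SDs 5/6/7/8, AR(1) correlation 0.7.** The weights for Weeks 16, 28, 40 and 52 are 0.743, 0.062, 0.055 and 0.139.

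- Slopes −0.040, −0.067, −0.093, −0.120: b* = −0.0558, so b52 − b* = −0.0642. Bias: 2 × (−0.0642) = −0.13 and 4 × (−0.0642) = −0.26 points.
- Slopes −0.05, −0.10, −0.15, −0.20: b* = −0.0795, so b52 − b* = −0.1205. Bias: −0.24 (δ = 2) and −0.48 (δ = 4).

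A simulation with these inputs (two groups of 80, baseline SD 15, 15% monotone dropout, known covariance, 300 runs) gave shifts between the two models of −0.14, −0.27, −0.26 and −0.51. Mean standard errors were 1.344 to 1.347 with the common slope and 1.349 to 1.359 with the by-visit slope. The largest shift is 0.51/1.35, about 0.4 standard errors.

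**Check 2: same slopes and AR(1), constant SD.** The weights become 0.385, 0.115, 0.115 and 0.385. Then b* is −0.080 or −0.125, b52 − b* is −0.040 or −0.075, and the bias is −0.08 and −0.16, or −0.15 and −0.30. How far early visits dominate depends on the covariance assumed.

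**Check 3: slopes derived from a model for FVC itself.** True-score SD 15, measurement-error SD 3, δ = 3:

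| Assumed course of FVC | b16 | b52 | b* | Bias at Week 52 |
|---|---|---|---|---|
| Random intercept only | −0.038 | −0.038 | −0.038 | 0.00 |
| Random slopes, SD 5/year, uncorrelated with level | −0.038 | −0.038 | −0.038 | 0.00 |
| Random slopes, SD 5/year, correlation +0.3 | −0.009 | +0.058 | −0.002 | +0.18 |
| Random slopes, SD 5/year, correlation −0.3 | −0.068 | −0.135 | −0.077 | −0.17 |
| Random slopes, SD 8/year, correlation −0.5 | −0.117 | −0.295 | −0.114 | −0.54 |
| 52-week correlation 0.95 | −0.054 | −0.087 | −0.063 | −0.07 |
| 52-week correlation 0.90 | −0.069 | −0.135 | −0.083 | −0.16 |
| 52-week correlation 0.80 | −0.102 | −0.231 | −0.125 | −0.32 |

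The bias is proportional to δ; at 5 points the range is −0.90 to +0.30.

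**Check 4: fitted MMRMs.** Maximum-likelihood fits with estimated unstructured covariance (70 per arm, δ = 3, true conditional difference 0, 300 runs), for the 0.90-correlation and SD 8/year cases, without dropout and with outcome-dependent dropout. The common-slope means were −0.23 to −0.66. The by-visit means were −0.05 to −0.13, with Monte Carlo standard error about 0.07 to 0.09, consistent with zero. The paired shift was −0.15 to −0.56. The SD of the estimate (common slope versus by-visit) was 1.28 v 1.28, 1.50 v 1.52, 1.49 v 1.40 and 1.53 v 1.46.

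**The case against.** The strongest reply is that the number carries no decision. There is no hypothesis, power or success criterion, everyone takes the same dose, and the primary objective, change from both Baselines, is met by descriptive summaries that do not use this slope. A main-effect baseline covariate, identical in both documents, is a legitimate choice. This stands as a limit on importance. It does not justify a bias that one model term avoids in an estimate that will appear with a confidence interval and p-value.

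The second reply is that bias needs two conditions together, neither documented, and that plausible models give exactly zero or the opposite sign. This also stands: the claim is that the estimate can be biased, not that it is.

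Three stronger inferences are tempting, and the documents support none of them:

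- *The earlier, less variable visits drive the pooled slope.* This depends on the covariance: the Week 16 weight falls from 74% to 38.5% when the SD is constant. The documents give no FVC SD or correlation.
- *Adding the term makes the prior-arm contrast unbiased.* It corrects one functional form. The comparison still conditions on a post-randomisation value among subjects who entered the extension, so it remains non-randomised.
- *The same imbalance affects the HZN-825 Baseline analysis.* That baseline precedes the first 301 dose. When it is the covariate the argument does not apply, apart from selection into the extension. SAP 9.1 says only that a similar process will be used and does not name the covariate.

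**Conclusion.** The point holds as a minor one. The model as written imposes one Trial Baseline slope on four visits, and the covariate is a 301 outcome that randomisation does not balance. The Week 52 LS mean difference is biased by (b52 − b*) × δ when the slope varies over visits and the prior arms differ at Trial Baseline. It is unbiased in this respect otherwise, and the sign is not fixed.

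Under the assumptions above the size is roughly 0.1 to 0.5 FVC points for gaps of 2 to 4 points. The most extreme course tried (SD 8/year, correlation −0.5) goes beyond that, at 4 × (−0.1805) = −0.72. Against a standard error of about 1.3 to 1.5 with 70 to 80 per arm, all of these are well under one standard error. A larger sample would shrink the standard error but not the bias. A reader should not infer that the primary result is materially wrong: the documents supply neither the slope pattern nor the gap, and the contrast is descriptive.

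**What to change.** In SAP 9.1 and Protocol 9.6.3, add *Trial Baseline by Visit Week* to the fixed effects, and do the same in the exploratory change-from-Trial-Baseline MMRMs that refer to 9.1. In the same edit, name the covariate in the HZN-825 Baseline model; the visit interaction is optional there if it is the pre-treatment value. It would also help to tabulate Trial Baseline FVC % predicted by prior arm and to state beside the LS mean differences that they are conditional on Trial Baseline and non-randomised.

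The cost is 3 degrees of freedom for endpoints measured at four visits and 1 for those measured only at Weeks 28 and 52. No new data are needed. The standard error rose by under 1% in one simulation; in the other, the SD of the estimate moved between about 1% up and 6% down.

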## 9.2 Exploratory Efficacy Endpoint Analyses

Analysis of the exploratory efficacy endpoints will be conducted in the order they are listed below for both changes from HZN-825 Baseline and Trial Baseline to Week 52 as needed.

The analysis will follow the primary analysis of the primary efficacy endpoint. The analysis will be based only on observed data.

Exploratory endpoints will be summarized at each time point. Change from HZN-825 Baseline and Trial Baseline will be evaluated separately.

### 9.2.1 Change from both Baselines in HAQ-DI at Week 52

The key exploratory efficacy endpoint is the change from both baselines in HAQ-DI.

The HAQ-DI assesses the subject's level of functional ability and includes questions of fine movements of the upper extremity, locomotor activities of the lower extremity, and activities that involved both upper and lower extremities. There are 20 questions in 8 categories of functioning including dressing, rising, eating, walking, hygiene, reach, grip, and usual activities [Cole et al., 2006]. The subject's ability to accomplish each activity in the past week is indicated as: without any difficulty, with some difficulty, with much difficulty, and unable to do. Any devices that are usually used to complete activities and any categories for which help from another person is needed are also assessed.

In addition, the subject will be asked the following anchor (additional) questions at the time points specified in Section 2.1 of the protocol:

How did your systemic sclerosis limit your daily activities in the last week?

- 0: did not limit activity
- 1: mildly limited my activity
- 2: moderately limited my activity
- 3: severely limited my activity
- 4: very severely limited my activity

How has limitation of your daily activities changed since the start of the trial?

- +3: very much less limited
- +2: much less limited
- +1: a little less limited
- 0: no change
- -1: a little more limited
- -2: much more limited
- -3: very much more limited

The HAQ-DI value itself is derived from a combination of the scores of the 8 categories of function and use of devices to result in one disability index, which ranges from 0 to 3 [Bruce B, Fries JF et al, 2003]. The HAQ-DI is calculated by scoring the answer to each question in the HAQ from 0 to 3, with 0 representing the ability to do without any difficulty, and 3 representing inability to do. Any activity that requires assistance from another individual or requires the use of an assistive device raises a 0 or 1 score to a 2. The highest score for each of the 8 domains is summed (range from 0 to 24) and divided by 8 to yield, on a scale with 25 possible values, a Functional Disability Index with a range from 0 to 3.

If a domain has all responses missing (including aids/devices) then the domain is considered missing. If some of the questions have a result and/or the aids/devices is checked, then use available values to calculate a domain score. The disability index is based on the number of domains answered and is computed only if the subject completes answers to at least 6 domains. That is, if 6 domains are non-missing, then the average of the 6 available scores will determine the Functional Disability Index. If < 6 domains are non-missing, then the HAQ-DI score will be missing.

If “Other” option is checked in either of the “AIDS AND DEVICES” sections of the questionnaire, the corresponding “Other, Specify” field will be reviewed and categorized by Horizon Therapeutics into an appropriate domain of function, so it can be incorporated into the score.

Analysis will follow that of the primary analysis of the primary efficacy endpoint, except that the analysis will be based only on observed data.

### 9.2.2 Change from both Baselines in MDGA at Week 52

The Physician Global Assessment (MDGA) is an 11-point scale ranging from 0 to 10 (0=excellent to 10=extremely poor) on which the physician rates the subject's overall health over the past week.

The MDGA will be tested in the same manner as that described for the primary analysis of the primary endpoint, but based only on observed data.

### **9.2.3 Change from both Baselines in PTGA at Week 52**

The Patient Global Assessment (PTGA) is an 11-point scale ranging from 0 to 10 (0=excellent to 10=extremely poor) on which the patient rates their overall health over the past week.

The PTGA will be tested in the same manner as that described for the primary analysis of the primary endpoint, but based only on observed data.

### **9.2.4 Change from both Baselines in the Physical Effects subscale of the SSPRO-18 at Week 52.**

The SSPRO-18 is an 18-item, patient-reported outcome instrument that specifically assesses skin-related quality of life in patients with SSc and was developed with extensive patient input and according to the FDA patient-reported outcomes guidance [Man et al., 2017]. The SSPRO-18 comprises 4 major conceptual constructs—physical effects, emotional effects, physical limitations and social effects—and has reproducibility and high internal consistency. This instrument reflects how subjects feel and function from several different health perspectives. Recall is the past 4 weeks. Response options are on a 0-6 point scale where 0 is ‘not at all’ and 6 is ‘very much.’ The physical effects or symptoms domain includes 5 items, physical limitations has 4 items, emotional effects includes 6 items and social effects has 3 items. A total score and domain specific scores (physical effects, physical limitations, emotional effects, and social effects) can be calculated and transformed to a 0 – 100 scale, with higher scores indicating more severe impact of skin problems on the patient’s quality of life. The SSPRO-18 Physical Effects subscale will be tested in the same manner as that described for the primary analysis of the primary endpoint, but based only on observed data.

Missing items will be imputed according to the instructions for the questionnaire. If the scoring manual for the SSPRO-18 does not indicate how to impute missing data, then the subscale with missing items will be considered missing.

### **9.2.5 Change from both Baseline in the Physical Limitations subscale of the SSPRO-18 at Week 52.**

The SSPRO-18 Physical Limitations subscale will be tested in the same manner as that described for the primary analysis of the primary endpoint, but based only on observed data.

Missing items will be handled as indicated in [Section 9.2.4](#)

### **9.2.6 Proportion of subjects with an mRSS decrease of $\geq 5$ points and 25% from both Baselines at Week 52.**

The mRSS is a validated method for estimating skin thickening [Khanna et al, 2017]. Seventeen different body areas are scored as normal (0), mild thickening (1), moderate thickening (2) and severe thickening (3). The scores selected for each body area are summed for a total score, which has a maximum score of 51.

Missing body area scores will be imputed according to the scoring instructions for this tool. If the scoring manual for the mRSS does not indicate how to impute missing data, then the body area with missing items and corresponding total score will be considered missing.

The proportion of subjects with an mRSS decrease in  $\geq 5$  points and 25% from both baselines at Week 52 will be analyzed with observed data using a stratified logistic regression model. Baseline value and treatment will be considered as factors in the model and use of mycophenolate mofetil [yes/no] and presence of ILD [yes/no]) will be considered as stratification factors. The probabilities of risk differences between each dose and reference group with its 95% confidence intervals will be presented. Subjects missing mRSS scores at Week 52 will be imputed as non-responders.

### **9.2.7 Responder rate (defined as ACR-CRISS [predicted probability] of at least 0.6) at Week 52**

Subjects will be evaluated using the ACR-CRISS, an outcome measure for diffuse cutaneous SSc. The ACR-CRISS includes core items that assess change in 2 prominent manifestations of early diffuse cutaneous SSc (skin and ILD), functional disability (HAQ-DI) and patient and physician global assessments. In addition, the score captures a clinically meaningful worsening of internal organ involvement requiring treatment.

The ACR-CRISS is a 2-step process that assigns a probability of improvement for a subject that ranges from 0.0 (no improvement) to 1.0 (marked improvement). Step 1 will be evaluated as part of the AE assessment, at which time the Investigator will assess if a subject has developed new or worsening cardiopulmonary and/or renal involvement due to SSc, as outlined below. Step 1 events will be adjudicated.

- New scleroderma renal crisis, defined as follows (adapted from Steen et al., 2003):  
Hypertensive scleroderma renal crisis:
  1. New onset hypertension, defined as any of the following:
    - a. systolic blood pressure  $\geq 140$  mmHg
    - b. diastolic blood pressure  $\geq 90$  mmHg

- c. rise in systolic blood pressure  $\geq 30$  mmHg
- d. rise in diastolic blood pressure  $\geq 20$  mmHg

AND

- 2. One of the following 5 features:
  - a. increase in serum creatinine by  $\geq 50\%$  over Baseline OR serum creatinine  $\geq 120\%$  of ULN for local laboratory
  - b. proteinuria  $\geq 2+$  by dipstick
  - c. hematuria  $\geq 2+$  by dipstick or  $\geq 10$  red blood cells/high-powered field
  - d. thrombocytopenia:  $<100,000$  platelets/mm $^3$
  - e. hemolysis, defined as anemia not due to other causes and either of the following:
    - 1. schistocytes or other red blood cell fragments seen on blood smear
    - 2. increased reticulocyte count

Normotensive scleroderma renal crisis:

- 1. Increase in serum creatinine  $>50\%$  over Baseline OR serum creatinine  $\geq 120\%$  of ULN for local laboratory:

AND

- 2. One of the following 5 features:
  - a. proteinuria  $\geq 2+$  by dipstick
  - b. hematuria  $\geq 2+$  by dipstick or  $\geq 10$  red blood cells/high-powered field
  - c. thrombocytopenia:  $<100,000$  platelets/mm $^3$
  - d. hemolysis, defined as anemia not due to other causes and either of the following:
    - 1. schistocytes or other red blood cell fragments seen on blood smear
    - 2. increased reticulocyte count
  - e. Renal biopsy findings consistent with scleroderma renal crisis (microangiopathy)
- Decline in FVC % predicted  $\geq 15\%$  (relative), confirmed by another FVC % within a month, high resolution computed tomography to confirm ILD (if previous scan did not show ILD) and FVC % predicted  $<80\%$  predicted;
- New onset of left ventricular failure (defined as ejection fraction  $\leq 45\%$ ) requiring treatment;
- New onset of pulmonary hypertension (PAH) on right heart catheterization requiring treatment.
- Gastrointestinal dysmotility requiring enteral (tube feeding) or parenteral nutrition

- Digital ischemia with gangrene, amputation, or hospitalization requiring treatment

If a subject meets any of these criteria, the subject is assigned a probability of 0. Otherwise, in Step 2, the probability of improvement is calculated based on the 5 core measures incorporated into the ACR-CRISS, including changes in mRSS, FVC % predicted, HAQ-DI, PTGA and MDGA [Khanna et al, 2016].

The predicted probability of improvement for each subject will be computed using the following equation in Step 2 (equation to derive predicted probabilities from a logistic regression model):

$$\frac{\exp(-5.54 - 0.81 * \Delta \text{MRSS} + 0.21 * \Delta \text{FVC\%} - 0.40 * \Delta \text{Pt-glob} - 0.44 * \Delta \text{MD-glob} - 3.41 * \Delta \text{HAQ-DI})}{1 + \exp(-5.54 - 0.81 * \Delta \text{MRSS} + 0.21 * \Delta \text{FVC\%} - 0.40 * \Delta \text{Pt-glob} - 0.44 * \Delta \text{MD-glob} - 3.41 * \Delta \text{HAQ-DI})}$$

where  $\Delta \text{MRSS}$  indicates the change in mRSS from Baseline,  $\Delta \text{FVC\%}$  denotes the change in FVC% predicted from Baseline,  $\Delta \text{Pt-glob}$  indicates the change in PTGA,  $\Delta \text{MD-glob}$  denotes the change in MDGA, and  $\Delta \text{HAQ-DI}$  is the change in HAQ-DI. All changes are absolute change (Time2 – Timebaseline). Subjects missing one or more components of the equation will be classified as non-responders. The MDGA and PTGA are the 11 point scales rating the subject's overall health during the preceding week by physician and patient, respectively.

If a subject does not have an event in Step 1 of the calculation and the equation in Step 2 shows a probability of at least 0.6 for an individual subject at Week 52, that subject will be classified as a responder; otherwise, the subject will be classified as a non-responder.

The responder rate by ACR-CRISS at Week 52 will be analyzed with a stratified logistic regression model. Both baselines value and treatment will be considered as factors in the model and use of mycophenolate mofetil [yes/no] and presence of ILD [yes/no]) will be considered as stratification factors. The probabilities of risk differences between each dose and placebo with its 95% confidence intervals will be presented.

### 9.2.8 Proportion of subjects with an improvement in $\geq 3$ of 5 core measures from both Baseline at Week 52

The proportion of subjects with an improvement in  $\geq 3$  of 5 core measures from both Baselines:  $\geq 20\%$  in mRSS,  $\geq 20\%$  in HAQ DI,  $\geq 20\%$  in PTGA,  $\geq 20\%$  in MDGA and  $\geq 5\%$  for FVC % predicted at Week 52 (ACR-CRISS-20) will be analyzed with the same model described in Section 9.2.7. The ACR-CRISS-20 is defined as  $\geq 3$  core measures of  $\geq 20\%$  in mRSS,  $\geq 20\%$  in HAQ DI,  $\geq 20\%$  in PTGA,  $\geq 20\%$  in MDGA and  $\geq 5\%$  for FVC % predicted.

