### **9.4 Treatments**

#### **9.4.1 Treatments Administered**

Subjects will receive fipaxalparant (HZN-825) 300 mg BID for 52 weeks.

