#### **9.4.7 Method of Assigning Subjects to Treatment Groups**

All subjects will receive fipaxalparant (HZN-825) 300 mg BID in this open-label extension trial.

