## **4.2 Study Treatments**

The dose regimen for all subjects will be HZN-825 300 mg twice every day for 52 weeks. Subjects will take 2 HZN-825 150 mg tablets orally in the morning and evening with a meal. Subjects will participate in a Safety Follow-up Visit 4 weeks after the last dose of HZN-825.

The treatment group will be based on randomized treatment in previous HZNP-HZN-825-301 trial and denoted as QD/BID (HZN-825 300mg QD/HZN-825 300mg BID), BID/BID (HZN-825 300mg BID/HZN-825 300mg BID), and PLC/BID (Placebo/HZN-825 300mg BID) accordingly.

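### SAP responder analyses: the comparator is called placebo in a trial without placebo, two missing-data rules conflict, and the baseline covariate for the composite endpoints is undefined

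*SAP*

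**What the plan says.** **Treatment and groups.** Protocol 9.4.7 states: "All subjects will receive fipaxalparant (HZN-825) 300 mg BID in this open-label extension trial". SAP 4.2 defines the analysis groups by the previous randomisation: "The treatment group will be based on randomized treatment in previous HZNP-HZN-825-301 trial and denoted as QD/BID", together with BID/BID and PLC/BID. SAP 9 describes the trial as open-label and single-arm, and treats group comparisons and p-values as descriptive.

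**Contrast.** For the ACR-CRISS responder, SAP 9.2.7 says: "The probabilities of risk differences between each dose and placebo with its 95% confidence intervals will be presented". For the mRSS responder, the matching sentence in SAP 9.2.6 reads "between each dose and reference group with its 95% confidence intervals will be presented", and no reference group is defined. SAP 9.2.8 (ACR-CRISS-20) takes over the 9.2.7 model.

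**Missing data.** In 9.2.6 the mRSS responder endpoint is to be "analyzed with observed data using a stratified logistic regression model", and the same paragraph ends: "Subjects missing mRSS scores at Week 52 will be imputed as non-responders". The opening of SAP 9.2 restricts all exploratory efficacy analyses to observed data. SAP 9.2.7 makes a subject with any missing component a non-responder. SAP 9.2.8 states no rule of its own. SAP 7 rules out imputation, with an exception for exploratory purposes.

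**Covariate.** In 9.2.7: "Both baselines value and treatment will be considered as factors in the model". No variable is named. Use of mycophenolate mofetil and presence of ILD are the stratification factors.

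**The concern.** Three things need correcting.

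1. A risk difference labelled as dose versus placebo reads as a placebo-controlled drug effect. Nobody receives placebo here and there is only one dose, so the number would be a difference between former arms that are all on the same active regimen.
2. Two rules for missing Week 52 data give two denominators, so both the response rate and the difference between groups depend on which sentence the programmer follows.
3. The composite endpoints are built only from changes from Baseline. A covariate described simply as their baseline value does not identify anything to put in the model.

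At stake are the size of the reported responder rates and the meaning that readers attach to the group differences.

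**Working it through.** The plan states no responder rate, dropout rate or sample size, so there is no figure to reproduce. The three items are checked in turn.

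**1. What the contrast can estimate.** With PLC/BID as comparator, two former-arm differences can be computed: QD/BID minus PLC/BID, and BID/BID minus PLC/BID. Their meaning depends on the Baseline.

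- From Trial Baseline, PLC/BID is in its first year on drug and the other two groups are in their second.
- From HZN-825 Baseline, PLC/BID has had placebo for 52 weeks and then drug for 52 weeks, while the others have had up to 24 months of drug (Protocol 7.2).

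Neither is drug against placebo. From Trial Baseline, an effective drug could even produce a negative difference, if most of the response comes in the first year of treatment.

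**2. Missing-data rule.** If missing counts as non-response and the FAS is the denominator, the rate is p × (1 − m), where p is the response rate among observed subjects and m is the fraction missing at Week 52. Under the observed-data rule the rate is p. All values of p and m are assumptions.

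| Observed-data rate p | m = 5% | m = 10% | m = 20% | m = 30% |
|---|---|---|---|---|
| 30% | 28.5% | 27% | 24% | 21% |
| 40% | 38% | 36% | 32% | 28% |
| 50% | 47.5% | 45% | 40% | 35% |

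The gap between the rules is p × m. It runs from 0.30 × 0.05 = 1.5 points to 0.50 × 0.30 = 15 points.

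The choice also affects group differences. Take two groups with the same observed rate of 40%, one with 10% and the other with 30% missing. The observed-data difference is 0. With missing as non-response it is 0.40 × 0.90 − 0.40 × 0.70 = 0.36 − 0.28 = 8 points. For common observed rates of 30% and 50% it is 6 and 10 points.

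**3. Baseline covariate.** The Step 2 equation in SAP 9.2.7 uses five changes and an intercept of −5.54. With every change set to zero, the score is exp(−5.54) / (1 + exp(−5.54)) = 0.0039 for every subject. A composite baseline is therefore a constant, that is, a multiple of the intercept column. A logistic design with an intercept, two group indicators, mycophenolate use, ILD and this constant has 6 columns and rank 5, so the covariate's coefficient cannot be estimated. Replacing the constant by a measured baseline such as mRSS gives rank 6. ACR-CRISS-20 (9.2.8) is also defined only by improvement from Baseline and has no baseline value. The mRSS responder endpoint in 9.2.6 is not affected, because mRSS itself is measured at Baseline.

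**The case against.** A reader might infer that these analyses cannot be run. The documents do not support that. SAP 4.2 supplies PLC/BID, so both contrasts are computable. A constant covariate would be aliased with the intercept and would leave the group contrasts unchanged. SAP 9.2.7 does not say that the covariate is an ACR-CRISS baseline; it names nothing, and five measured component baselines exist.

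A reader might also take the wording to put both Baselines into one model. SAP 9.2 says that changes from the two Baselines are evaluated separately, so separate models are the more natural reading.

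Another tempting reading is that stratified logistic regression means conditional logistic regression, which cannot deliver a risk difference. The SAP does not say conditional. SAP 9.1 enters the same two factors as fixed covariates and SAP 9.2 tells the exploratory analyses to follow it, so an ordinary adjusted model is plausible, and it can give a standardised risk difference. What stands is that the step from model to risk difference is not described.

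The placebo wording is in 9.2.7 and reaches 9.2.8 through the shared model; 9.2.6 does not use it. How the output tables will be labelled is unknown, because the table shells are not among the documents.

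On missing data, the explicit rule in 9.2.7 could be taken to override the general sentence in 9.2, and SAP 7 allows imputation for exploratory purposes. That softens the conflict with SAP 7. It does not settle the two instructions within 9.2.6, nor does it amend the observed-data restriction in 9.2.

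Finally, the endpoints are exploratory and SAP 9 makes the comparisons descriptive, so no error rate or trial decision depends on them.

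**Conclusion.** Two rules are wrong as written. The comparator in 9.2.7 does not exist in this trial, and 9.2.6 gives two incompatible missing-data instructions for one endpoint, while 9.2 and 9.2.7 disagree on the same matter. A third item, the baseline covariate for the composite endpoints, is undefined.

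The first item changes what the contrast means, not whether it can be computed. The second changes the reported rate by 1.5 to 15 points, assuming 30% to 50% observed response and 5% to 30% missing; these ranges are illustrative. The third leaves a modelling choice open and would not by itself distort the group contrasts. The claims that the analyses cannot be run, or that the model is conditional, go beyond the text.

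The matter is worth correcting before database lock. Its weight is limited by the exploratory status of the endpoints.

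**What to change.** - **Comparator (9.2.6 to 9.2.8).** Name the contrasts QD/BID versus PLC/BID and BID/BID versus PLC/BID. State that they are descriptive former-arm differences, not placebo-controlled effects. Lead with the responder proportion and its 95% CI for each former group and overall, separately for each Baseline; this fits Protocol 9.6.3, which plans descriptive summaries by former group and overall.
- **Missing data.** Apply one rule to all responder endpoints: missing counts as non-response, with the FAS as denominator. This matches what 9.2.7 already does. Delete the reference to observed data in 9.2.6, and add an exception for responder endpoints to the observed-data sentence in 9.2; without that exception the contradiction remains.
- **Covariate (9.2.7, 9.2.8).** Use measured component baselines, for example mRSS and FVC % predicted, taken from the Baseline being analysed, with one Baseline per model; or drop the covariate.
- **Estimate.** State whether the risk difference comes from a standardised logistic model or from a Mantel-Haenszel estimate across the mycophenolate and ILD strata.
- **Carry-over.** SAP 3 bases the plan on Protocol 2.2. Protocol 3.0 no longer lists ACR-CRISS-20 and adds a CRISS 25 responder endpoint, so any CRISS 25 section that replaces 9.2.8 should take the same corrections.

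The cost is rewording of the SAP and matching edits to the table shells. No data collection or trial conduct changes.
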